## MEDICAL PROTOCOL (HRP-590)

### PROTOCOL TITLE: Brivaracetam to Reduce Neuropathic Pain in Chronic SCI: A Pilot Clinical Trial

VERSION DATE: 03/18/2024

consequences of living with paralysis. Recent studies indicate that the resting state sensorimotor network is disrupted after SCI [Hou et al., 2014] and that the development of chronic pain has a physiologic basis in altered brain structure and function. Specifically, individuals with SCI display decreased inter-hemispheric functional connectivity between the bilateral primary sensorimotor cortex, as well as increased intra-hemispheric functional connectivity within the motor network. Further, Nicotra et al [Nicotra et al., 2006] found that people with SCI displayed enhanced responses within dorsal anterior cingulate cortex and periaqueductal gray during the processing of threat. After SCI, there are also rapid and extensive reductions in gray matter volume in the primary somatosensory cortex lower body, leg, and foot areas [Solstrand Dahlberg et al., 2018]. The degree of atrophy likely depends on the level and completeness of the lesion, the time since injury, and on the presence of pain, but there is disagreement as to how these factors may interact. In a longitudinal study over the first 12 months post SCI, Freund et al. found gray matter volume reductions in the leg area of the primary motor cortex, but not the somatosensory cortex [Freund et al., 2013], and progressive reductions over time were observed in the thalamus, anterior cingulate, secondary somatosensory cortex, insula and pons [Ziegler et al., 2018]. Such changes in volume related quantitatively to sensory deficits, but there were no correlations between neuropathic pain and volumetric declines during the first year of injury. On the other hand, Jutzeler et al. reported reductions in anterior cingulate cortex (ACC), insula, secondary somatosensory cortex, and thalamus volume in SCI patients with and without neuropathic pain compared to controls. Neuropathic pain was associated with increases in ACC and primary motor cortex gray matter, as well as reductions in primary somatosensory cortex and thalamic gray matter [Jutzeler et al., 2016]. Although inconclusive, the above studies indicate that structural reductions rapidly occur in both cortical (sensorimotor cortex, ACC, insula) and subcortical (hippocampus, thalamus, pons) areas following SCI that seem to be influenced by time since injury and the clinical state (i.e. presence of neuropathic pain).

**microRNA and Neuropathic Pain.** microRNAs (miRNA) have emerged as important biomarkers and molecular mediators in numerous physiological and pathological settings. miRNAs are short, non-coding single-stranded RNA molecules with the ability to exert post-transcriptional modulation of large sections of the genome by binding to regulatory gene elements and inhibiting the translation of many genes [Bartel, 2009; Lagos-Quintana et al., 2001]. They bind to untranslated regions of genes with sometimes imperfect complementarity, which allows for one specific miRNA molecule to inhibit the translation of multiple genes. They are found in every human tissue and biofluid, are resistant to RNase degradation and have the ability to cross the blood brain barrier making them an excellent choice as a biomarker for neuro-trauma related conditions, neuro-recovery, and response to various therapeutic interventions [Liu and Paroo, 2010].

## MEDICAL PROTOCOL (HRP-590)

### PROTOCOL TITLE: Brivaracetam to Reduce Neuropathic Pain in Chronic SCI: A Pilot Clinical Trial

VERSION DATE: 03/18/2024

Significant alterations in microRNAs expression (together with the resultant changes in protein expression) have been reported in both the affected tissues and in the blood from patients suffering from several pain conditions such as complex regional pain syndrome, cystitis-induced chronic pain and irritable bowel disorder. Spinal cord injury-induced neuropathic pain represents a significant clinical challenge that affects 20-77% of injured persons. Specific changes in protein expression in peripheral nociceptive and central neurons are thought to contribute to the development of hyper-excitability which is at the basis of the genesis and persistence of chronic neuropathic pain [Gold and Gebhart, 2010]. Because SCI-induced neuropathic pain is mediated by, among other factors, neuronal protein expression, the process can potentially be regulated by miRNAs. Many studies have been conducted in rodent models of neuropathy investigating changes in miRNA expression both centrally and peripherally. Most of them have demonstrated dysregulation in numerous miRNAs [Bali et al., 2014; Genda et al., 2013; Wu et al., 2011]. In one particular study [Imai et al., 2011], the authors found that a lesion in the periphery (sciatic nerve) caused downregulation of specific miRNA centrally (in post-synaptic neurons of nucleus accumbens). Furthermore, the authors proposed that these changes may be involved in the development of co-morbid conditions like anxiety and sleep disorders, typically associated with persistent pain stimuli. Despite some discrepancies in the literature of this emerging research field, there is a general consensus in that miRNA alterations that occur both in the CNS and the PNS mediate or are associated with neuropathic pain.

The study of miRNA in neuropathic pain is a relatively new field of research. However, the significance of miRNA alterations in a variety of rodent pain models and in clinical conditions characterized by pain has been clearly established (there are more than 30 publications in 2019 alone). The majority of these studies have been conducted in animal models. However, a few studies also describe changes in miRNAs-signatures in complex regional pain syndrome [Orlova et al., 2011] and irritable bowel syndrome-patients [Zhou et al., 2010]. There is evidence that a specific miRNA might play a role in the pathogenesis of neuropathic pain in SCI. miR-485 regulates presynaptic expression of SV2A and regulates dendritic spine density and synapse morphology and function [Cohen et al., 2011]. Synaptic plasticity is a homeostatic response essential to adapt neural circuit connectivity and excitation in response to neurotrauma. miRNA-485 expression is regulated in a number of neurological diseases and after brain trauma. For instance, miRNA-485 is down-regulated in Huntington disease [Packer et al., 2008], Alzheimer's disease [Cogswell et al., 2008], and traumatic brain injury [Redell et al., 2009]. These disease studies, together with our findings that SV2A expression is increased in individuals with neuropathic pain, suggest that decreased levels of miR-485 with corresponding increased levels of SV2A and neural network activity in nociceptive neurons may contribute to the pathophysiology of SCI-induced neuropathic pain.

Because miR-485 regulates SV2A expression, the target of brivaracetam, we hypothesize that circulating miR-485 may be a valuable predictive biomarker of response to therapy.

## MEDICAL PROTOCOL (HRP-590)

PROTOCOL TITLE: Brivaracetam to Reduce Neuropathic Pain in Chronic SCI: A Pilot Clinical Trial  
VERSION DATE: 03/18/2024

That is, we hypothesize that individuals with lower circulating miR485 levels may be less likely to respond to brivaracetam treatment for neuropathic pain than those with higher circulating miR485.

miRNAs are promising molecules with potential use as prognostic and diagnostic biomarkers of neuropathic pain and also as predictive biomarkers to monitor the effect of treatments for neuropathic pain in humans. However, the lack of properly conducted clinical studies prevents the bench-to-bedside translation of this knowledge to the clinical setting. This project aims to address these gaps by studying the role of miRNA in SCI neuropathic in humans as well as miRNA signatures as predictive biomarkers of response to brivaracetam therapy in SCI. This evidence provides the scientific rationale for the studies proposed in Aim 3.

### **3.0 Study Endpoints/Events/Outcomes**

#### **3.1 Primary Endpoint/Event/Outcome:**

Our primary endpoints will be 1) safety as determined by number of drug related adverse events and assessed through weekly adverse event screening by phone, and 2) efficacy as determined by reduction in pain intensity assessed by the Brief Pain Inventory. We will use the clinically meaningful reduction in Brief Pain Inventory score of 1 point or more as the definition of “drug response” in this study.

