## 5.0 Procedures Involved

### 5.1 Study Design:

This is a multi-center randomized, double-blinded placebo-controlled pilot clinical trial. Each site (Swedish Medical Center/Craig Hospital, UMN) will enroll and study 20 adults, 18 years of age and older with SCI. [name] will serve as PI, and [name] will serve as Co-I at UMN (local site). MRI data analysis will be conducted by [name] (Harvard University). [name] will receive a deidentified dataset and will have no human subject interactions. Research activities at the Swedish Medical Center/Craig Hospital will be conducted under a separate IRB protocol at Craig Hospital.

Participants who meet the eligibility criteria will be randomly assigned to active drug (escalating brivaracetam dose to 100 mg twice daily for 3 months) or placebo based on a randomization schedule developed by our biostatistician. This is a simple computer generated 1:1 scheme that randomly assigns participants to arm A or arm B. Study participants, research coordinators, and study personnel involved in outcomes assessments and analyses will all be blinded. The drug will be provided by RxArtisans pharmacy in Wayzata, MN. The active and placebo capsules will have identical appearance and consistency. Treatment assignment will be known only to the investigational drug pharmacies (RxArtisans). We have registered this pilot study with National Institutes of Health (NIH) clinical trials registry, [www.clinicaltrials.gov](http://www.clinicaltrials.gov) (NCT04379011). The pilot data generated by this effort will be used to power a subsequent multi-center clinical trial.

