CDE-recommended questionnaires relating to pain, mood, active suicidality, satisfaction with life, kinesiophobia, sleep quality, and community integration will be administered. Participants will then begin 3 months of active treatment (100 mg BID) or placebo. All participants will receive a medication diary to track study drug compliance and to record medication use. Blinded data collectors will perform weekly check-in calls to assess for medication-related adverse events including the PHQ-9 for changes in mood and suicidality. Reported AEs identified in these calls will be documented and immediately shared with the PI for review.

End of study assessments will be repeated 3 months after baseline testing and again 1 month after cessation of study medication (active/placebo).

Lab work will be repeated to confirm normal renal function, absence of liver cirrhosis, and absence of pregnancy in individuals of childbearing potential at the end of the study. Specimen collection and analysis will either occur at the Fairview Clinical Research Unit or with the participant's

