## MEDICAL PROTOCOL (HRP-590)

PROTOCOL TITLE: Brivaracetam to Reduce Neuropathic Pain in Chronic SCI: A Pilot Clinical Trial  
VERSION DATE: 03/18/2024

primary care provider, based on participant preference. Participants will receive \$150 after baseline testing, \$150 after end of study testing sessions and \$50 after the 1-month post drug cessation follow-up to compensate them for their time and to assist with transportation.

Our primary endpoints will be safety (# of drug related adverse events) and efficacy (reduction in pain intensity assessed by the Brief Pain Inventory). We will use the clinically meaningful reduction in Brief Pain Inventory score of 1 point or more as the definition of “drug response” in this study. Secondary outcomes include change in mood, satisfaction with life, community integration, and brain resting state functional connectivity. All fMRI data will be deidentified and sent by secure server to Harvard Medical School for analysis by [name] (consultant) as is done in our ongoing collaborative studies (Effects of Ekso-assisted gait training on Bone Health and Quality of Life: A Randomized Clinical Trial, PI [name]).

*Suicide Protocol:* Endorsement of active suicidality on PHQ-9 will trigger the suicide protocol. 911 will be called in the event of a psychological emergency noted during a phone call (credible report of intent to harm oneself). Study staff will first ask to speak to another adult in the household. If none is present or comes to call, study staff will call 911 and remain on the line until first responders arrive. In the event of a non-emergent psychological situation (psychological distress in the absence of intent for self-harm), study staff will refer the participant to their PCP or the National Suicide Hotline ([name]). In either case, study staff will notify the PI immediately.

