### *15.1 Data Analysis Plan:*

For aim 1, the main outcome variables of interest include various dimensions of pain, mood (PHQ-9), life satisfaction (SWLS), resting state brain connectivity, and community integration (CHART-SF) measured at baseline and again at 3-months of treatment. Of particular interest is whether there is a difference in pain reduction from baseline to end of study between the treatment and control groups; this will be analyzed in this pilot with linear regression including terms for group and time and the interaction of group by time. We note that many of these instruments have bounded scores and we will include analyses that recognize these (via, e.g., non- linearities or recognize the bounds such as Tobit regression) Further exploratory analyses will examine the relationships (correlations) between changes in pain and changes in mood, life satisfaction, resting state brain connectivity, and community integration using linear regression.

For aim 2, we will use the same analytic approach we have refined in our 2 active rsfMRI studies. MRI data will be analyzed using the SPM12 based Conn toolbox 3 (Version 17f, Matlab R2018b). Preprocessing steps include realignment and unwarping, slice-timing correction, ART based identification of outlier scans for scrubbing, segmentation and normalization to MNI space, and 8 mm smoothing. Denoising steps include scrubbing, aCompCor, ICA-based denoising, Global Regression, and 0.008 to 0.09 Hz band-pass filtering). Three main comparisons will be evaluated: The effect of drug treatment on rsfMRI measures, the effect of pain intensity on rsfMRI measures (each via linear regression as in Aim 1), and the differences in rsfMRI measures between active drug responders and non-responders; this last will also be analyzed via linear regression; note, however, that this will be limited to those in the active group and people in the placebo group will not be included. First, we will evaluate region-of-interest (ROI) based functional connectivity in a set of anatomically defined regions known to be impacted in SCI and neuropathic pain: the periaqueductal gray, the bilateral thalamus, the amygdala, the hippocampus, the insula, anterior cingulate, the precentral and the post-central gyrus. Second, we will evaluate, on a voxel-by-voxel basis, amplitude of low frequency fluctuations (ALFF) and intrinsic resting state functional connectivity.

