## MEDICAL PROTOCOL (HRP-590)

PROTOCOL TITLE: Brivaracetam to Reduce Neuropathic Pain in Chronic SCI: A Pilot Clinical Trial  
VERSION DATE: 03/18/2024

participation in the study. The medical monitor will also indicate whether he concurs with the details of the report provided by the study investigator. Reports for events determined by either the investigator or medical monitor to be possibly or definitely related to participation, and reports of events resulting in death will be promptly forwarded to the IRB and FDA.

Reporting Adverse Events. Anticipated adverse events (detailed above in 13.0, Risks to Participants) will be identified while interviewing participants, during physical exams, and while reviewing laboratory results. Participants also will be directed to call study staff to report adverse events that may occur between these visits. All adverse events will be noted on the Adverse Events log form that will be kept in the participant's file. Unanticipated adverse events and unanticipated serious adverse events (as defined in CFR Title 21), also will be identified during testing time points and through participant self-reporting between these visits. They will be noted on the Adverse Events Log and promptly brought to the attention of the study PI.

Unanticipated serious adverse events will be reported within 5 working days to the UMN IRB as required.

Follow-up of Adverse Events. In the unlikely event that a participant is injured as a result of this research study, medical care, including emergency treatment will be provided.

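### The primary safety endpoint is a raw count of events judged drug-related, with no participant-level unit, repeat rule or attribution criteria, and Section 15 plans no adverse-event analysis by arm

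*Combined protocol and SAP*

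**What the plan says.** Section 3.1 defines the first primary endpoint as "safety as determined by number of drug related adverse events and assessed through weekly adverse event screening by phone". Section 5.2 repeats it: "Our primary endpoints will be safety (# of drug related adverse events) and efficacy" (the pain endpoint follows). Specific Aim 1 asks whether the drug is safe as well as effective.

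The Aim 1 analysis in section 15.1 opens: "For aim 1, the main outcome variables of interest include various dimensions of pain". It goes on to mood, life satisfaction, brain connectivity and community integration. Adverse events are not listed. The only between-arm tests of counts or proportions in Section 15 are those in 15.3, for participant characteristics.

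On collection, section 5.2 states: "Blinded data collectors will perform weekly check-in calls to assess for medication-related adverse events". Section 18.2 is broader: "All adverse events will be noted on the Adverse Events log form that will be kept in the participant's file". Relatedness wording appears in 18.2 only to govern expedited reporting: "Reports for events determined by either the investigator or medical monitor to be possibly or definitely related to participation". It is not tied to the endpoint.

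On blinding, section 5.1 says: "Study participants, research coordinators, and study personnel involved in outcomes assessments and analyses will all be blinded". It adds that only the pharmacy knows the assignment, whereas 18.2 heads its paragraph on the medical monitor as unblinded and has that monitor comment on relatedness of serious events and deaths.

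**The concern.** A count of events is not a count of people. In a small trial with weekly contact, a total can reflect one participant's persistent symptom instead of the arm's experience. No rule says a continuing symptom is counted once.

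The relatedness filter adds a second problem. Section 13.1 lists somnolence and fatigue, depression, constipation, loss of balance and anxiety as foreseeable risks. In people with spinal cord injury, severe pain and other pain medicines, each of these can have another cause. A blinded assessor cannot reliably tell the causes apart in one person, but the randomised placebo arm can do so on average. Filtering before comparing gives up part of that advantage, by an unknown amount because no criteria are stated.

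At stake is whether the pilot delivers what section 15.2 says it is for, namely estimates for planning a follow-up trial. A total of related events gives neither an incidence per participant nor a precision for it.

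**Working it through.** The documents give no adverse-event rate, safety threshold or power figure, so there is nothing of the plan's own to reproduce. Event rates, dispersion and example counts below are assumptions for illustration.

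**Inputs from the documents**
- Participants per arm under 1:1 allocation: section 5.1 has 20 at each of two sites, so 40/2 = 20; section 23.1 has 20 study-wide, so 20/2 = 10. Both are carried.
- Weekly calls: the dosing steps in 4.1 sum to 14 + 14 + 48 = 76 days, and 76/7 = 10.9. Three months is about 91 days, and 91/7 = 13. So about 11 to 13 calls.

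**One participant against the total.** Suppose one active participant reports the same symptom on all 13 calls, each report is entered as an event, and every other affected participant has one event. The p-values are an exact binomial test on totals (null proportion 0.5) and Fisher's exact test on participants.

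| Per arm | Event totals | p | Participants affected | p | That person's share of the active total |
|---|---|---|---|---|---|
| 10 | 13 + 2 = 15 v 3 | 0.008 | 3/10 v 3/10 | 1.0 | 13/15 = 87% |
| 20 | 13 + 4 = 17 v 6 | 0.035 | 5/20 v 6/20 | 1.0 | 13/17 = 76% |

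**Less extreme clustering.** In 20,000 simulations with identical arms, counts were gamma-Poisson with variance m + m²/k and mean m = 1 event per participant.
- With k = 1 or 0.5, the largest single contributor supplied on average 24% or 30% of all events at 10 per arm, and 14% or 18% at 20 per arm.
- A nominal 5% test on raw totals rejected 3–4% of the time with no clustering, 12–13% at k = 1 and 19–22% at k = 0.5.
- Fisher's test on participants with at least one event stayed at or below 2.6% in every setting run.

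The plan names no test for this endpoint, so these rejection rates show how a bare total behaves and are not errors in a planned analysis.

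**The filter.** Let b be background and d drug-caused events per participant, and let s_b and s_d be the fractions of each judged related, with s_b equal in both arms under blinding. Expected related events per participant are s_b·b on placebo and s_b·b + s_d·d on active, so the difference is s_d·d. It equals d if every drug-caused event is recognised (s_d = 1) and d/2 if half are (s_d = 0.5). The documents give no value for s_d.

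**Precision of the participant-level estimate.** For an assumed 50% v 30% with at least one event, the Newcombe interval, built from Wilson limits for each arm, is:
- 10 per arm: limits 0.237–0.763 and 0.108–0.603. Lower = 0.20 − √(0.263² + 0.303²) = −0.20; upper = 0.20 + √(0.263² + 0.192²) = 0.53.
- 20 per arm: limits 0.299–0.701 and 0.145–0.519. Lower = 0.20 − √(0.201² + 0.219²) = −0.10; upper = 0.20 + √(0.201² + 0.155²) = 0.45.

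The result would be descriptive either way.

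**The case against.** A reader might infer that the endpoint throws away the placebo comparison. The documents do not support that. The trial is double-blind, blinded collectors make the calls, and events can be labelled drug-related in either arm. Nothing says the count is pooled, limited to the active arm or withheld from tabulation by arm. What can be said is that no comparison is specified and that the filter may weaken one.

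A reader might also infer that a continuing symptom will be re-entered each week. The documents are silent on this. Thirteen entries from one person is a worst case that the silence permits.

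The attribution worry has a counter-argument that partly stands. Because 13.1 names these symptoms as foreseeable risks, assessors may lean towards calling them drug-related. Mood is also captured without attribution, through the PHQ-9. The direction and size of any misattribution are therefore unknown.

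Two further figures should not be used. With mean 2 and k from 2 to 0.5, √(1 + m/k) gives 1.4 to 2.2 as the factor by which treating counts as independent understates the standard error, but the plan never proposes such an analysis and 15.2 promises robust standard errors throughout. The exact upper limit when no events are seen, 1 − 0.025^(1/n) = 31% for 10 and 17% for 20, depends only on sample size and applies equally to the proposed measure.

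Finally, this is a pilot, and the Revision History records enrolment as complete at version 8.0. That argues for adding an analysis instead of replacing a primary endpoint. It does not excuse leaving a primary endpoint without one.

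**Conclusion.** The concern holds as a gap in definition and analysis. A primary endpoint is stated as a raw, attribution-filtered number of events, with no participant-level unit, repeat rule or relatedness criteria, and Section 15 plans no adverse-event analysis by arm. At 10 or 20 per arm one participant can dominate the total: in the worst case illustrated, 76–87% of an arm's events. Under moderate to strong clustering at mean 1, the largest contributor supplies on average 14–30% of all events. These sizes rest on assumed rates and dispersion and, for the worst case, on each weekly report being entered as a new event. The loss from the relatedness filter is proportional to the share of drug-caused events judged unrelated, which the documents do not allow one to estimate. The point does not invalidate the trial and can be put right in the analysis.

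**What to change.** In 3.1, 5.2 and 15.1, add as the main safety analysis:
- the number and percent of randomised, dosed participants in each arm with at least one treatment-emergent adverse event of any cause, taken from the all-event log in 18.2, with exact 95% CIs per arm and a risk difference with its 95% CI;
- serious events, and events leading to dose reduction or stopping, reported the same way;
- a rule that a continuing symptom counts once.

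Keep the drug-related event count as supportive, with stated relatedness criteria applied blind to arm. Reconcile 5.1 with the unblinded monitor in 18.2, and 5.1 with 23.1 on total sample size. Mean events per participant would not serve as the main measure: it is the total divided by n, so one person can still dominate it. If an event rate per person-week is also shown, exact binomial limits do not apply to it.

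The cost is wording and one table. Because enrolment is complete, date the change and say whether it was made before allocation was known to the analysts. There are two drawbacks. Background events will appear in both arms. And because the weekly calls are described as assessing medication-related events, all-cause capture may be incomplete, which should be reported as a limitation.

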#### Specific Aims:

1. Specific Aim 1: Determine whether a 3-month course of daily brivaracetam is safe and effective at reducing severe below-level neuropathic pain after SCI.
2. Specific Aim 2: Determine whether a 3-month course of daily brivaracetam decreases periaqueductal gray activity in SCI.
3. Specific Aim 3: Determine whether baseline microRNA levels are associated with response to brivaracetam treatment.

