*Modified Brief Pain Inventory (BPI) – main outcome.* The BPI is a short self-assessment questionnaire that provides information on various dimensions of pain including how pain developed, the types of pain a patient experiences, and time of day pain is experienced, as well as current ways of alleviating pain [Cleeland and Ryan, 1994]. The BPI also consists of the VAS Pain scale, a simple 10-point scale (0 = “no pain”, 10 = “pain as bad as you can imagine”) measuring a patient’s worst pain and least pain, on average and at present time. The Brief Pain Inventory provides information on the intensity of pain (the sensory dimension) as well as the degree to which pain interferes with function (the reactive dimension). According to several previous studies on pain in spinal cord injury, the BPI is an effective measure [Bryce et al., 2007].

*International Spinal Cord Injury Pain Data Set.* This tool assesses average pain intensity in the last week using a 0-10 numerical rating scale. The 1-10

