7.2.3 Future analysis of genotypes: N/A

## 8.0 Study Population

### 8.1 Inclusion Criteria:

- 18 years of age or older
- Completed inpatient rehabilitation and living in the community
- Ongoing severe below-level neuropathic pain (daily average 9/10 or 10/10)
- Tried and failed to achieve adequate pain relief with the use of other drugs (previous pain management drugs failed to decrease their pain below a self-reported level of 9 out of 10)

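### A 1-point fall in BPI is labelled drug response and used to split the active arm in one Aim 2 comparison, although a substantial share of participants could show that fall with no drug effect

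*Combined protocol and SAP*

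**What the plan says.** Sections 3.1, 4.1 and 5.2 all define drug response as a "clinically meaningful reduction in Brief Pain Inventory score of 1 point or more"; none gives a basis for the cut. Section 8.1 admits people with "Ongoing severe below-level neuropathic pain (daily average 9/10 or 10/10") whose earlier drugs did not bring pain below 9. Section 5.2 describes the BPI pain rating as "a simple 10-point scale" anchored at 0 and 10 and lists four ratings, "worst pain and least pain, on average and at present time", without saying which of them, or what mean of them, defines response.

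The label is used in Section 15.1. The third of three Aim 2 comparisons is "the differences in rsfMRI measures between active drug responders and non-responders", and "this will be limited to those in the active group and people in the placebo group will not be included". The text does not say whether the imaging measures are those at baseline or their change, although Section 1.1 names baseline periaqueductal gray activity as a candidate marker of response. Pain itself is compared between arms by "linear regression including terms for group and time and the interaction of group by time". Aim 3 is to "Determine whether baseline microRNA levels are associated with response to brivaracetam treatment", but its analysis text names no responder split.

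**The concern.** Selection at the top of a bounded scale makes a later fall likely whether or not the drug works. On a single 0-10 item, 1 point is the smallest possible fall. Section 5.2 also lets other pain medication continue, which is another route to a 1-point fall unrelated to study drug. To call every such fall a drug response attributes to brivaracetam what may be background change. In the Aim 2 comparison nothing corrects for this, because the placebo arm, which would show the background rate, is excluded.

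Two further costs follow. Cutting a continuous change at one value discards information in a very small sample. And a marker that goes with improvement among treated people may simply go with improvement in anyone, so the comparison cannot show that the marker predicts response to the drug. The pilot exists to supply estimates for a larger trial, and these marker estimates are among them.

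**Working it through.** The plan states no power, effect size, placebo rate or SD of change, so there is no figure to reproduce.

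**1. Rate of 1-point falls with no drug effect.** From the documents: entry at 9 or more, 0-10 integer ratings, fall of at least 1. Assumed: true pain normal in the source population; each rating equals true pain plus error of SD s, rounded and held within 0-10. One source population is the mean 3.0, SD 2.5 sample in Section 2.2 (unselected SCI, range 0-8, so only a guide); the others are assumptions. Simulated percentage with a fall of at least 1, shown as fresh baseline / entry rating used as baseline:

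| Mean, SD | s = 0.5 | s = 1.0 | s = 1.5 |
|---|---|---|---|
| 3.0, 2.5 | 22 / 37 | 32 / 58 | 38 / 70 |
| 6, 2 | 20 / 33 | 31 / 52 | 36 / 62 |
| 7, 1.5 | 22 / 37 | 32 / 55 | 37 / 63 |
| 8, 1.5 | 20 / 29 | 29 / 44 | 33 / 52 |

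The range is 20-38% with a fresh baseline and 29-70% with the entry rating as baseline. Over a wider grid (means 6-8, SDs 1.5-2.5) it is 13-39% and 18-73%.

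**2. Cross-check without rounding or selection.** If change is normal with mean fall m and SD d, P(fall ≥ 1) = 1 − Φ((1 − m)/d). For m = 0 and d from 0.7 to 2.5 this is 8-35%; for m = 0.5 it is 24-42%. Averaging items lowers it: with m = 0 and d = 1 for one item the rate is 1 − Φ(1) = 16%; for a mean of four items with independent errors d = 0.5, giving 1 − Φ(2) = 2%. Correlated item errors would put it in between.

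**3. What the label would contain.** Suppose 30% fall 1 point anyway and the drug adds 20 percentage points. Then 0.30/0.50 = 60% of labelled active responders would have met the rule without drug. For background rates of 20-40% and added rates of 10-30 points the share is 40-80%.

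**4. Information lost by the split.** Relative efficiency at responder proportion q is φ(z)²/(q(1 − q)), with z the normal quantile of q.
- q = 0.5: 0.399²/0.25 = 0.64, a loss of 36%.
- q = 0.3: 0.348²/0.21 = 0.58, a loss of 42%.
- q = 0.2: 0.280²/0.16 = 0.49, a loss of 51%.

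**5. Active-arm power, two-sided 5%.** Section 23.1 gives 20 participants in total and Section 5.1 gives 20 at each of two sites, so about 10 or 20 are active under 1:1 allocation. Assumed: mean true change 1, SD 1.5, rating error 0.7, marker correlated 0.5-0.7 with true change.
- 10 active: continuous change 22-46%, split 15-28%.
- 20 active: continuous change 47-81%, split 31-58%.

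With 10 active and 20% responders, the chance that one group has fewer than 2 people is about 0.8¹⁰ + 10 × 0.2 × 0.8⁹ = 0.107 + 0.268, or 38%. MRI is optional (Section 5.2), so the Aim 2 numbers may be smaller still.

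**6. Marker-by-arm term, same assumptions.** With the marker unrelated to change on placebo and an assumed placebo true-change SD of 0.5-1.5, power is about 13-33% at 10 per arm and 25-65% at 20 per arm.

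**The case against.** The strongest reply is that little rests on the label. Efficacy is judged by a group-by-time regression against randomised placebo, which deals with regression to the mean between arms. The split is one of three Aim 2 comparisons; another relates pain intensity to the imaging measures, and Aim 1 correlates change in pain with change in connectivity. Section 15.2 says that estimation, not significance, is the main purpose. All of this stands. It does not rescue the responder comparison: change-on-change correlations do not address baseline markers of response, and a plan built on estimation is ill served by an estimate that discards information and has no comparator.

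A reader might infer more than the documents support:
- *That Aim 3 uses the same split.* Its analysis text compares placebo with treated samples and group means; only the aim statement speaks of response.
- *That responder groups would be mostly noise.* Under the power model in step 5, 1.5²/(1.5² + 2 × 0.7²) = 2.25/3.23 = 70% of the variance of observed change is true change. The high background rates in step 1 need larger rating errors or the entry rating as baseline.
- *That a marker-by-arm model recovers the lost power.* Step 6 shows that it does not. Its merit is that it answers the predictive question.
- *That 1 point is the wrong clinical threshold.* That is not at issue here.

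It is also fair that Section 8.1 asks for an ongoing daily average, which is steadier than the single rating simulated. That favours the lower part of the ranges.

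**Conclusion.** The point holds in limited form. The definition, the entry level and the active-only split are all in the text. A substantial share of participants could be labelled drug responders with no drug effect: about 20-38% with a fresh baseline and 29-70% if the entry rating is the baseline. These figures rest on an assumed within-person SD of 0.5-1.5 and a single BPI item; very stable ratings or a multi-item mean would lower them. The information loss of 36-51% does not depend on rating error, only on a roughly normal change and 20-50% responders. The lack of a placebo comparator follows from the text alone.

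The damage is confined to the Aim 2 responder comparison, and to Aim 3 only if response is analysed there by the 1-point rule. The between-arm pain regression and the planned correlations of pain change with connectivity change are untouched, and no stated power target is missed.

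**What to change.** - Rename the 1-point rate *1-point improvement* in Sections 3.1, 4.1 and 5.2. Report it descriptively in both arms, with the between-arm difference.
- Name the BPI item, or the mean of items, that is used, and state which rating is the baseline.
- In the Aim 2 responder comparison, replace the split with continuous BPI change. Report the active-arm association for precision.
- Add a both-arm model with a marker-by-arm term for the predictive question, reported as an estimate with confidence interval. State that this interaction is imprecise at this sample size and does not itself raise power.
- Apply the same to Aim 3 only where response is analysed.

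The cost is wording. Enrolment is complete according to the revision history, and the change needs no new data, visits or software. The downside is that a simple responder picture is no longer the main display, though it can still be shown as a description.
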